Systemic adverse events reported during the studies and judged to be possibly related to the study product and/or delivery device have been generally mild to moderate in severity and include flu-like symptoms, headache, fever, nausea, chills, dizziness, malaise, fatigue, arthralgia, myalgia, neuralgia, and aphthous stomatitis. Several subjects have reported individual instances of severe fatigue within 24 hours of dosing, all of which resolved by the following day. Mild to moderate transient hematological abnormalities have been observed in a small number of subjects during the studies and have included white blood cell count, red blood cell count, hemoglobin, absolute neutrophils, absolute monocytes, absolute lymphocytes, and platelets. Likewise, serum chemistry abnormalities have been generally mild to moderate in severity and transient in duration. These have included ALT/AST, creatine phosphokinase, creatinine, non-fasting glucose, estimated glomerular filtration rate (eGFR). Among these, elevation in serum creatine phosphokinase of mild to moderate severity in small minority of subjects has judged to be potentially associated with procedure administration. One instance of Grade 4 hypoglycemia was reported in one subject and was diagnosed as an unrecognized pre-existing condition.

TDS-ID device:

Systemic adverse events judged to be at least possibly related to the vaccine candidate or the TDS-ID administration procedure were all grade 1 or 2 and included fatigue, headache, low grade fever, dizziness, enlarged lymph nodes, elevated blood pressure. In rare cases, syncope has been reported in subjects receiving intramuscular injections with the TDS technology (TDS-IM V1.0). Monitoring for these and other systemic symptoms commonly seen in investigational vaccine studies (eg, fever, chills, rash, nausea, and allergic reaction) will be performed throughout the study and addressed as required to maximize subject safety.

No serious systemic adverse events attributed to the device or administration procedure have been observed to date during any of the clinical studies utilizing the TDS-ID device.

4.5.1.3. DNA Vaccine Investigational Product Risks

It is important to note that this protocol investigates a combination product, which is the DNA vaccine product together with the TDS delivery device, and that risks for the 2 may necessarily need to be considered as a single phenomenon, and could be hard to attribute to either product or device.

The systemic reactions that have been reported in previous studies using the investigational vaccines with these and other devices included fatigue, headache, tachypnea, and myalgia. Light-headedness/dizziness, which in one case progressed to syncope, has also been reported. Monitoring for these and other systemic symptoms commonly seen in investigational vaccine studies (eg, fever, chills, rash, nausea, and allergic reaction) will be performed throughout the study and addressed as required to maximize subject safety.

Research from this program has shown that these DNA vaccines do not cause infection with the target viruses, nor do they cause integration of the vaccine DNA into the test subject.

The HTNV and PUUV DNA vaccines do not contain live virus and encode only a portion of the HTNV and PUUV viral genome, which is insufficient to support production of live virus. Therefore, there is no basis to expect that these candidates may cause infection. The FDA considered safety measurements appropriate based on results of preclinical and clinical studies performed using DNA vaccines with the same plasmid backbone (pWRG7077). Persistence analysis in a study using a similar DNA vaccine vector indicated that the presence of vaccine DNA 30 to 90 days after administration was confined to the tissues at the site of administration (muscle and skin), and only at very low (ie, < 1,000 copies/µg) levels, suggesting minimal risk for potential integration of vaccine DNA into host DNA ([Dolter et al, 2011](#)). The TDS-ID also describes acceptable biodistribution safety data for the VEE vaccine based in the pWRG-7077 backbone, which is the vector used in this study. In addition, the Center for Biologics Evaluation and Research (CBER) guidance entitled *Considerations for Plasmid DNA Vaccines for Infectious Disease*, dated November 2007, stipulates that “biodistribution studies may be waived for DNA vaccines produced by inserting a novel gene into a plasmid vector previously documented to have an acceptable biodistribution/integration profile.”

4.5.1.4. Pregnancy

Risks to unborn babies are unknown at this time; pregnant females will be excluded from this study.

Sexually active men² and women³ of childbearing potential must be using an effective method of contraception from 30 days prior to the first study vaccination until 6 months after the last study vaccination.

All female subjects of childbearing potential must be abstinent or utilize effective contraceptive precautions. Non-childbearing potential is defined as either surgically sterilized or 1 year post-menopausal (defined as 12 consecutive months without menses). Study subjects should not become pregnant during the study and for at least 6 months after the last study vaccination.

Last, participants who are in non-male sexual relationships, abstaining from sexual intercourse with a male partner, or are in a monogamous sexual relationship with a vasectomized partner satisfy the study requirement to avoid pregnancy 30 days prior to the first study vaccination until 6 months after the last study vaccination (see inclusion criteria).

4.5.1.5. Lactation

Risks to nursing infants are unknown at this time; lactating females will be excluded from this study.

4.5.1.6. Venipuncture

Blood sampling carries a minimal risk of minor discomfort and the possibility of minor bruising at the site of the needle puncture and, rarely, the possibility of infection at the needle puncture site. Venipuncture causes transient discomfort and may result in fainting. Fainting is usually transient and managed by having the subject lie down and elevate his/her legs. Bruising at the site of the venipuncture may occur but may be prevented or lessened by applying pressure to the site for several minutes. Venipuncture may also cause infection. The use of aseptic (sterile) technique will make infection at the site where blood will be drawn extremely unlikely.

4.5.1.7. Allergic Reaction

As with any Investigational New Drug (IND) product administration and no matter what precautions are taken, there is always the risk of a serious, or even life-threatening, allergic reaction. To mitigate this risk, potential subjects with a history of severe allergic reaction of any kind, or significant allergic reaction to a known component of the experimental products, will be excluded from participation. Medical emergency equipment is located at the University of

² A sexually active man is defined as one whose partner is a woman of childbearing potential (see definition below) and has not had a vasectomy performed > 1 year prior to screening must agree not to father a child until 6 months after the last vaccination. These subjects must agree to use a barrier method of birth control (eg, either condom with spermicidal foam/gel/film/cream or partner usage of occlusive cap [diaphragm or cervical/vault caps] with spermicidal foam/gel/film/cream/suppository).

³ Women of childbearing potential are defined as those who have not been sterilized via tubal ligation, bilateral salpingectomy, bilateral oophorectomy, hysterectomy, or successful Essure® placement (permanent, non-surgical, non-hormonal sterilization) with history of documented radiological confirmation test at least 90 days after the procedure (or with use of another birth control method if history of confirmation test not confirmed), still menstruating or < 1 year of the last menses if perimenopausal. For this study, an effective contraceptive method is defined as one that results in a failure rate of less than 1% per year when it is used consistently and correctly.

Maryland Center for Vaccine Development. This is available to handle emergencies, such as anaphylaxis, angioedema, bronchospasm, and laryngospasm.

4.5.1.8. Guillain-Barré Syndrome

Guillain-Barré syndrome (GBS) is a disorder in which the body's immune system attacks part of the peripheral nervous system. It afflicts only about one person in 100,000, and in rare instances vaccinations may increase the risk of GBS. The first symptoms of this disorder include varying degrees of weakness or tingling sensations in the legs. These symptoms can increase in intensity until certain muscles cannot be used at all. Most individuals recover from even the most severe cases of Guillain-Barré syndrome, although some continue to have a certain degree of weakness ([NIH, 2011](#)). To mitigate this risk, individuals with a history of GBS, other neurologic diseases per the physician investigator's discretion, or other significant reaction to vaccination will be excluded from participation.

4.5.1.9. Unknown Risks

Furthermore, as with all research there is the remote possibility of risks that are unknown or that cannot be foreseen based on available information. This would include late effects that have been seen with some vaccines. The long-term effects on EP-mediated delivery of DNA is not known.

4.5.2. Alternatives to This IND Product or Study

At this time, there is no known alternative to taking this product to afford the same potential protection from HFRS. An alternative is not to participate in this study.

4.5.3. Intended Benefit for Subjects

There is no intended direct benefit for study subjects.

4.5.4. Risks to the Study Personnel and the Environment

The principal risk in the clinical setting is (eg, in the handling of needles that may be contaminated and the attendant risks including hepatitis, human immunodeficiency virus (HIV), and other human pathogens). Adherence to standard operating procedures (SOP) for working with infectious agents and universal precautions will reduce the risk of exposure.

Injury to operators is possible if the electroporation devices are handled improperly; therefore, these devices are for use only by qualified medical personnel who have completed a training course on the set up and use of the TDS systems.

There are no known risks to the environment other than those associated with the generation of biohazardous waste attendant to HTNV and PUUV vaccination of humans. All biohazardous waste will be disposed of as stipulated by local, state, and Federal regulations and in accordance with study site SOPs.

4.5.5. Risks to Subject Confidentiality

Efforts will be made to keep subject personal information confidential within the limits of the law. There is a small risk of loss of confidentiality by an unauthorized person viewing subject records. In order to maintain confidentiality, study physicians and the study team will store study

records in a limited-access, locked office. Subject personal information may be disclosed if required by law to authorized representatives of relevant organizations including the US Army Medical Research and Development Command USAMRDC, the National Institutes of Health (NIH), the Institutional Review Board (IRB) at the University of Maryland, and/or the Federal Drug Administration (FDA), who will be allowed to inspect sections of medical and research records related to the study. The risks of storing subject samples for use in possible future research studies or having them used in future research studies are those associated with possible loss of confidentiality. Subject samples will be labeled only by a code and will not be labeled with subject name or other personal identifying information.

4.6. Route of Administration, Dosage Regimen, Treatment Period, and Rationale

Subjects will receive HTNV DNA vaccine, pWRG/HTN-M(co), and PUUV DNA vaccine, pWRG/PUU-M(s2), administered separately and as a mixture using the TDS-IM V1.0 or TDS-ID devices developed by Ichor Medical Systems, Inc. Subjects will be randomized to the following 6 groups and will receive 1 dose on Days 0, 28, and 56 for a total of 3 doses. The vaccine mixing process will be outlined in a supplementary Pharmacy Manual. [Table 3](#) shows the investigational product dosage, schedule, and mode of administration.

Table 3: Investigational Product Dosage, Schedule, and Mode of Administration

Group	Product	Dose/Route	Dilution Preparation	Injection Volume	Dose Administration
Group 1	HTNV	0.6 mg/ID EP	0.1 mL 6.0 mg/mL HTNV DNA + 0.1 mL 0.9% saline	0.2 mL	Days 0, 28, and 56
Group 2	HTNV	3.0 mg/IM EP	0.5 mL 6.0 mg/mL HTNV DNA + 0.5 mL 0.9% saline	1.0 mL	Days 0, 28, and 56
Group 3	PUUV	0.6 mg/ID EP	0.1 mL 6.0 mg/mL PUUV DNA + 0.1 mL 0.9% saline	0.2 mL	Days 0, 28, and 56
Group 4	PUUV	3.0 mg/IM EP	0.5 mL 6.0 mg/mL PUUV DNA + 0.5 mL 0.9% saline	1.0 mL	Days 0, 28, and 56
Group 5	HTNV/PUUV	1.2 mg/ID EP (0.6 mg each)	0.1 mL 6.0 mg/mL HTNV DNA + 0.1 mL 6.0 mg/mL PUUV DNA	0.2 mL	Days 0, 28, and 56
Group 6	HTNV/PUUV	6.0 mg/IM EP (3.0 mg each)	0.5 mL 6.0 mg/mL HTNV DNA + 0.5 mL 6.0 mg/mL PUUV DNA	1.0 mL	Days 0, 28, and 56

The rationale for dosages and plan of administration is based on prior work by the delivery device manufacturer and prior experience from a previous HTNV DNA and PUUV DNA

vaccine study in which candidate vaccines were shown to elicit antibodies in humans when administered by IM EP.

4.7. Compliance Statement

The study will be conducted according to the US Code of Federal Regulations (CFR) applicable to clinical studies (45 CFR Part 46, 21 CFR Part 50, 21 CFR Part 56, and 21 CFR Part 312), the study protocol and in compliance with International Council for Harmonisation (ICH) Good Clinical Practice (GCP), Belmont Principles, and other applicable regulatory and Department of Defense (DoD) requirements. All identified study personnel will be trained to perform their roles and will carry out their responsibilities in accordance with ICH GCP guideline and clinic site SOPs. Roles and responsibilities of study staff are presented in [Appendix A](#).

4.8. Study Population

The study population may consist of as many as 82 healthy male and nonpregnant, nonlactating female subjects, ages 18 to 49 years (inclusive), who are HTNV and PUUV naïve.

Refer to Section [11.2](#) for a statistical justification of the sample size.

4.9. Study Site

The study will be performed at the University of Maryland Center for Vaccine Development.

5. TRIAL OBJECTIVES AND PURPOSE

5.1. Primary Objective

- To evaluate the safety and reactogenicity of the HTNV, PUUV, and HTNV/PUUV DNA vaccine candidates delivered to healthy adults either IM or ID by EP.

5.2. Secondary Objectives

- To obtain a preliminary assessment of the immunogenicity of the combination HTNV/PUUV DNA vaccine candidate relative to the monovalent formulations.
- To identify the HTNV and/or PUUV DNA vaccine combination and route of administration that elicits the most immunogenic response as determined by seroconversion and seropositivity rates, and geometric mean titers (GMT) as measured by PsVNA50.

6. TRIAL DESIGN

6.1. Study Endpoints

Primary endpoints, correlating to the primary objective of the study, will include determining the nature, frequency, and severity of AEs and/or SAEs associated with TDS-EP-based administration of HTNV, PUUV and HTNV/PUUV DNA vaccines.

- The occurrence of solicited local and systemic AEs occurring from the time of each injection through 14 days following the procedure
- The occurrence of vaccine-related unsolicited AEs from the time of the first injection through 28 days following each injection
- The occurrence of SAEs from the time of the first injection through the final study visit (approximately 6 months post-last vaccination)
- The occurrence of clinical safety laboratory AEs through 14 days following each study vaccination

Secondary endpoints, correlating to the secondary objectives of the study will be to determine the proportion of seropositive subjects ($\text{PsVNA50} \geq 1:20$) and the final overall rate of seroconversion over all scheduled time points to study completion for each study group. GMT will be calculated using PsVNA50 .

- Determination of the proportion of seropositive subjects (defined as $\text{PsVNA50} \geq 1:20$) at each scheduled time point (eg, Days 0, 28, 56, 84 and 140)
- Determination of the final overall rate of seroconversion over all scheduled time points to study completion for each study group. Seroconversion is defined as a post-vaccination HTNV- or PUUV-specific titer of $\geq 1:40$, or a minimum four-fold rise compared to baseline titer, and all study volunteers will begin the study with a baseline titer < 20 (ie, seronegative).
- Determination of GMT of the PsVNA50 for HTNV- and PUUV-specific neutralizing antibodies at each scheduled time point for each study group and over all time points for each study group.

Exploratory endpoints, evaluated as part of the immunogenicity objectives, including calculation of PsVNA80 titers for HTNV and PUUV may be calculated from the collected data for informational purposes, and neutralization assays using other hantavirus PsV (eg, Seoul virus, Dobrava virus) may also be performed to evaluate levels of cross-neutralizing antibodies.

- Determination of GMT of neutralizing of the PsVNA80 for HTNV- and PUUV-specific neutralizing antibodies at each scheduled time point for which blood samples are taken for each study group and over all time points for each study group
- Determination of GMT of neutralizing of the PsVNA80 for Seoul- and Dobrava-specific neutralizing antibodies at each scheduled time point for which blood samples are taken for each study group and over all time points for each study group

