^c Safety lab results will not be reviewed prior to product administration, and inclusion/exclusion criteria will be applied, with the exception of exclusion criteria 9, which will not be applied for vaccinations 2 and 3 because it is for screening prior to enrollment.

^d Physical examination will be completed at screening visit 1, and includes examination of general appearance, skin, neck (including thyroid), eyes, nose, throat, lungs, heart, abdomen, lymph nodes, extremities, and a basic neurological assessment; directed physical exams will be completed at all other visits. A directed physical exam is defined as a focus, complaint-driven physical examination. In the absence of a complaint, a physical exam will not be performed.

^e Reactogenicity assessments will include subject completion of a memory aid each day for 14 days after a vaccination visit.

^f Vital sign measurements include oral temperature, heart rate, respiratory rate, and systolic and diastolic blood pressure.

^g Complete blood count (CBC [WBC, Hb, platelets] with differential), glucose, creatinine, AST, ALT, total bilirubin. Lab abnormalities will be followed up on an ad hoc basis as per the study investigators. At Screen 1, a collection of 2.7 mL blood will be used to perform the PT/PTT tests to determine any coagulation abnormalities for exclusion criterion 25.

^h Blood will be drawn prior to study product administration. Safety lab results will not be reviewed prior to product administration.

ⁱ Approximately 10 mL of blood will be collected at Screen 2 to determine subject eligibility.

^j Blood collected for the humoral immune response to vaccination will be approximately 10 mL on Days 0, 28, 56 and 140; any remaining blood will be stored for future use. Approximately 50 mL of blood will be collected on Day 84 for humoral immune response to vaccination and for future use.

For determination of any cardiac abnormalities, an ECG will be performed at Screen 1 and study visit 11.

ⁿ Procedures will be completed only if Screen Visit 2 falls outside of the 56-day screening window prior to vaccination. See Section 8.1.2 for further clarification

^o Scripted telephone contact for collection of Serious Adverse Event information

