8.1.3. Vaccination Visits

There will be 3 primary vaccination visits: Day 0, Day 28 ± 4 days, and Day 56 ± 4 days. Subjects will receive up to 3 vaccinations in the outer aspect of the subject's upper arm (deltoid area; alternating arms, beginning with left, if possible), using the TDS-IM V1.0 or TDS-ID EP system during the course of the study. Vaccine composition, vaccine dose and schedules (per group), subject randomization, and the TDS EP system have been discussed earlier in this protocol.

The following procedures will be performed during each vaccination visit:

- Review subject's medical history including concomitant medication use since screening or previous vaccination
- Review eligibility criteria with subjects and safety criteria including AEs, prior to study vaccination to ensure continued eligibility (see Section 7.5)
- Do a directed physical examination if indicated based on the subject's interim medical history (see also [Table 4](#)). Assess injection site prior to study vaccination to establish a baseline.

- Take resting vital sign measurement including oral temperature, heart rate, respiratory rate, and systolic and diastolic blood pressure. Subjects must not eat or drink anything hot or cold, or smoke within 10 minutes prior to taking oral temperature.
- Weigh subject, and if there is a $> 15\%$ change in body weight, measure skinfold thickness at potential injection sites with a caliper
- Perform a buccal swab for human leukocyte antigen (HLA) testing (Day 0 only)
- Collect approximately 22.5 mL of whole venous blood for the determination of:
 - CBC (WBC, Hb, platelets) with differential
 - Glucose, Cr, AST, ALT, total bilirubin
 - HTNV and PUUV-specific antibody as measured by PsVNA, using approximately 10 mL of the total 22.5 mL blood
- Urine sample collection for determination of pregnancy (must be negative prior to administration of the vaccine)
- Injection with study product
- Post-injection observation period/reactogenicity assessment (Subjects will be kept under observation for at least 30 minutes after each inoculation to ensure their safety, and any reactions during this period will be documented. Appropriate medical equipment and emergency medications, including epinephrine [1:1000], will be available on site in the event of an anaphylactic or other immediate allergic reaction.)
 - Give subject ruler and thermometer and explain how to use (Day 0 only)
 - Distribute memory aid and teach them how to complete memory aid

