8.1.4. Follow-Up Visits

There will be 9 follow-up visits: Day $2 + 1$ day, Day 14 ± 2 days, Day 30 ± 1 day, Day 42 ± 2 days, Day 58 ± 1 day, Day 70 ± 2 days, Day 84 ± 4 days and Day 140 ± 7 days and D220 Phone Call ± 14 days

The following procedures will be performed during each follow-up visit (some exceptions):

- Review of subject's medical history (including concomitant medications and AE) since previous visit
- Directed physical examination (injection site) if indicated based on the subject's interim medical history

- Take resting vital sign measurement including oral temperature, heart rate, respiratory rate, and systolic and diastolic blood pressure. Subjects must not eat or drink anything hot or cold, or smoke within 10 minutes prior to taking oral temperature.
- Review and collect memory aids (Days 14, 42, 70)
- Collect approximately 12.5 to 72.5 mL (depending on the scheduled visit day, see [Table 4](#)) of whole venous blood for the determination of:
 - CBC (WBC, Hb, platelets) with differential (Days 14, 42, and 70 only)
 - Glucose, Cr, AST, ALT, total bilirubin, (Days 14, 42, and 70)
- Collect blood for determination of HTNV- and PUUV-specific antibodies as measured by PsVNA assay (Days 84 and 140)
- Collect approximately 50 mL of blood for future research on Day 84 only
- Collect blood sample for determination of pregnancy test (Day 140 only)
- Perform ECG as last assessment of cardiac normality (Day 140 only)

Day 140 will be the final scheduled in-clinic visit for all subjects

Serious Adverse Event Final Telephone Follow Up Visit

There will be a scripted telephone follow up visit conducted at Day 220 ± 14 days.

- Review and collection of serious adverse events occurring since last visit conducted at Day 140.

Early Termination Visits

If a subject leaves the study early (see also Section [7.5](#)), procedures pertaining to Day 140 in the follow-up visit section (Section [8.1.4](#)) will be followed:

- Review of subject's medical history (including concomitant medications and AE) since previous visit
- Directed physical examination (injection site) and resting vital signs check (oral temperature (no recent hot or cold beverages or smoking), heart rate, respiratory rate, and systolic and diastolic blood pressure)
- Review and collection of any remaining memory aids
- HTNV- and PUUV-specific antibodies (PsVNA50 for final visit)
- Serum sample collection for determination of pregnancy test
- Perform ECG

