10.3.1. Adverse Event or Suspected Adverse Reaction

ICH E6 Good Clinical Practice Guidelines define an adverse event (AE) as any untoward medical occurrence in a patient or clinical investigation subject administered a pharmaceutical product regardless of its causal relationship to the study treatment. An AE can therefore be any unfavorable and unintended sign (including an abnormal laboratory finding), symptom, or disease temporally associated with the use of medicinal (investigational) product.

An AE is considered to be any adverse change or exacerbation from a baseline condition that occurs following the initial administration of an investigational product whether or not the event is considered to be related to the investigational product. Examples of this include but are not limited to the following:

- Adverse changes including new signs and symptoms, intercurrent illness modifying the clinical course, or the worsening of a baseline condition including the increased frequency of an event or an increased intensity of a condition
- Concomitant disease with onset or increased severity after the start of study product administration
- A new pattern in a preexisting condition, occurring after the receipt of investigational product that may signal a clinically meaningful change
- Clinically significant changes in laboratory values

Suspected adverse reaction means any adverse event for which there is a reasonable possibility that the drug caused the adverse event. For the purposes of IND safety reporting, “reasonable possibility” means there is evidence to suggest a causal relationship between the drug and the adverse event. Suspected adverse reaction implies a lesser degree of certainty about causality than adverse reaction, which means any adverse event caused by a drug.

Adverse events will be documented in terms of a medical diagnosis. When this is not possible, the adverse event will be documented in terms of signs and/or symptoms observed by the investigator or reported by the subject at each study visit. AEs occurring while on study will be documented appropriately regardless of relationship. Information to be collected include event

description, date of onset, clinician's assessment of severity, relationship to study product (assessed only by those with the training and authority to make a diagnosis), and date of resolution/stabilization of the event. All AEs will be followed to adequate resolution or stabilization.

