8.8. Clinical Laboratory Evaluations

Clinical Safety Laboratory testing will be performed at the following study visits: Screens, 1, 3, 4, 6, 7 and 9. (Listing 1.7)

For hematology and serum chemistry tests, any clinically significant changes from baseline value will be identified and reported.

The median, interquartile range, and normal values for each laboratory values (as determined by the contract laboratory) will be reported for each treatment group for each specimen collection point.

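### The primary laboratory-AE endpoint leaves out the pre-dose safety labs on Days 28 and 56, and no rule says which dose an abnormality first seen there belongs to

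*Protocol*

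**What the plan says.** Protocol 6.1 lists among the primary endpoints "The occurrence of clinical safety laboratory AEs through 14 days following each study vaccination". Protocol 10.2 and SAP 3.3 give the same window.

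The laboratory schedule is in SAP 8.8: "Clinical Safety Laboratory testing will be performed at the following study visits: Screens, 1, 3, 4, 6, 7 and 9". In Protocol Table 4 those visits after screening are Days 0, 14, 28, 42, 56 and 70. Three of them are dosing days: "There will be 3 primary vaccination visits: Day 0, Day 28 ± 4 days, and Day 56 ± 4 days" (Protocol 8.1.3). On those days, footnote h to Table 4 states: "Blood will be drawn prior to study product administration. Safety lab results will not be reviewed prior to product administration". Protocol 8.1.4 gives the follow-up windows: "Day 14 ± 2 days, Day 30 ± 1 day, Day 42 ± 2 days, Day 58 ± 1 day, Day 70 ± 2 days". It restricts follow-up safety labs to Days 14, 42 and 70, so none is drawn on Day 84.

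Two other provisions bear on the point. Another primary endpoint is "The occurrence of vaccine-related unsolicited AEs from the time of the first injection through 28 days following each injection" (Protocol 6.1). Protocol 10.3.1 names among its examples of an AE "Clinically significant changes in laboratory values".

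**The concern.** The trial draws and tests blood immediately before doses 2 and 3, yet its laboratory endpoint closes about two weeks earlier. A graded abnormality that first appears on Day 28 or Day 56 is therefore outside the endpoint meant to count such events. Neither document says how to attribute it.

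Two things are at stake. The laboratory-AE tally may understate later-onset changes after doses 1 and 2. Also, no per-dose baseline is defined, so a value already abnormal before dose 2 or 3, and still abnormal at the next 14-day draw, lies inside the later dose's window with nothing in the endpoint to mark it as pre-existing. In a three-dose study at dose levels not previously given to humans, the reader of the safety tables needs to tell these apart.

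**Working it through.** The plan attaches no sample size, power or event count to this endpoint, so there is no stated figure to reproduce. The check is date arithmetic.

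**Inputs.** Doses on Day 0, Day 28 ± 4 and Day 56 ± 4 (Protocol 8.1.3). Labs on Days 14, 42 and 70, each ± 2 (Protocol 8.1.4), and before dosing on Days 28 and 56 (Table 4, footnote h).

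**Formula.** For a draw on day d with window w, after a dose on day D with window W, and with windows counted from Day 0: earliest gap = (d − w) − (D + W); latest gap = (d + w) − (D − W). For Day 56: 52 − 32 = 20 and 60 − 24 = 36. The documents do not say whether windows run from Day 0 or from the actual dose date. For the second reading the gap is (d − D) ± w.

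| Draw | Preceding dose | Nominal gap (days) | Range, windows from Day 0 | Range, windows from actual dose | Can be ≤ 14? |
|---|---|---|---|---|---|
| Day 14 | 1 | 14 | 12–16 | 12–16 | yes |
| Day 28, pre-dose 2 | 1 | 28 | 24–32 | 24–32 | no |
| Day 42 | 2 | 14 | 8–20 | 12–16 | yes |
| Day 56, pre-dose 3 | 2 | 28 | 20–36 | 24–32 | no |
| Day 70 | 3 | 14 | 8–20 | 12–16 | yes |

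**Result.** The smallest possible gaps for Days 28 and 56 are 24 and 20 days. Both exceed 14, and both draws precede the dose given that day, so neither falls in any dose's window. That is 2/5 = 40% of scheduled post-baseline draws. At the maximum of 82 subjects with full attendance it is 2 × 82 = 164 of 5 × 82 = 410.

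**A related gap.** A compliant Day 14, 42 or 70 draw can fall on day 15 or 16 after the dose (up to day 20 for Days 42 and 70 with windows from Day 0), and then also misses a literal 14-day limit. SAP Table 2.2 uses 16 days for solicited and 32 days for unsolicited AEs; the laboratory endpoint has no such allowance.

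**Illustration only.** Assume onset is uniform over Days 0–56 and each abnormality lasts L days, with L at most 14. The counted draws (14 and 42) then detect 2L/56. Adding Days 28 and 56 gives 4L/56.

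| L (days) | Counted draws | All four draws |
|---|---|---|
| 7 | 14/56 = 25% | 28/56 = 50% |
| 10 | 20/56 = 36% | 40/56 = 71% |
| 14 | 28/56 = 50% | 56/56 = 100% |

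At the other extreme, if every abnormality starts early enough to be seen by the 14-day draw, leaving out Days 28 and 56 loses nothing.

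**The case against.** A reader might infer that Day 28 and Day 56 abnormalities are lost, or are charged to the next dose. The documents support neither.

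On loss: AEs are collected from first dose to study end (Protocol 10.6.1). Laboratory results are to be summarised by severity and study day (Protocol 11.1.1, SAP 8.5), and Listing 1.7 shows each value with its planned time point and actual day. A clinically significant, vaccine-related change can count in the 28-day unsolicited endpoint, and SAP Table 2.2 reaches 32 days with a column for all AEs regardless of relatedness. This stands, within limits. The 28-day endpoint is confined to vaccine-related events, and by date of draw a sample on days 29–32 is past it. The tables in Protocol 11.1.2 compare baseline with the final value only, and SAP 8.8 gives medians and interquartile ranges. The SAP's table mock-ups contain no laboratory table, and Listing 1.7 has no grade column.

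On charging to the next dose: no text directs it. Onset dates are recorded, and a value found before dosing on Day 28 has an onset no later than that day. With a 21-day abnormality, for example, every onset between Days 14 and 28 is still present at the Day 28 draw and so is documented before dose 2. No mock-up tabulates laboratory AEs by dose. What remains is a risk: draw and dose share a date, and Listing 1.11.2 carries onset date and dose number but no time, so a date-only derivation could pick the wrong dose.

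It is also fair to say that 14 days is the only laboratory follow-up common to all three doses, that uniform onset describes background abnormalities better than vaccine effects, and that the SAP calls all analyses exploratory (SAP 5). These points limit the size of the problem and shape the fix. They do not bring the two draws into the endpoint.

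**Conclusion.** The point holds for the laboratory-AE endpoint as worded. It excludes 2 of 5 scheduled post-baseline draws under every permitted visit window, a result that needs no assumption beyond the schedule. The 164 of 410 count assumes 82 subjects with full attendance.

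A graded value first seen at those draws stays in the database and in the by-day reporting, and may be counted as a vaccine-related unsolicited AE within 28 days. If it is judged not clinically significant or not vaccine-related, it is in neither of these two primary endpoints. Attribution to a dose is left open, and misattribution is possible rather than planned.

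How many events this moves cannot be known from the documents. The 25–50% against 50–100% detection figures rest on an assumed uniform onset and should not be read as an estimate of missed vaccine effects. The change is worth making because it alters a primary safety tally at very little cost; it does not call the trial's safety data into question.

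**What to change.** In the Protocol Synopsis, 6.1 and 10.2 and in SAP 3.3, define the endpoint as graded laboratory AEs at any scheduled draw after the first vaccination: Days 14, 28, 42, 56 and 70, each with its visit window. That also settles the day 15–16 problem. Then state in the SAP:

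- The Day 28 and Day 56 samples are pre-dose, and their values are attributed to the preceding dose whatever the calendar date.
- A value after dose 2 or 3 counts as new only if its grade exceeds that of the pre-dose sample for that dose: Day 28 is the reference for Days 42 and 56, and Day 56 for Day 70.
- Results are reported by draw and overall by group. This needs one laboratory table among the mock-ups and a grade column in Listing 1.7.

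**Cost.** Wording and one table shell; every sample is already scheduled and tested. The count may rise slightly with background abnormalities. Doses 1 and 2 would have two draws each against one for dose 3, because no safety lab follows Day 70. Any comparison by dose should therefore use only the 14-day draws (Days 14, 42 and 70).
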